6.4 Investigator responsibilities

All non-serious AEs, whether expected or not, should be recorded in the patient's medical notes. Only non-serious AEs which constitute a notifiable event (listed in section 6.2) should be reported to CCTU (via the trial database) within 5 working days.

All Foreseeable SAEs that are **casually related** to the trial intervention (NEL) or trial procedures should be reported to CCTU immediately and no later than 24 hours after the site staff becomes aware of the event.

All Unforeseeable SAEs (regardless of causal relationship to trial intervention NEL or trial procedures) should be reported to CCTU immediately and no later than 24 hours after the site staff becomes aware of the event.

Please refer to Appendix II for Safety Reporting Flowchart.

6.4.1 Investigator Assessment

6.4.1.1 Seriousness

When an AE occurs, the investigator responsible for the care of the participant must first assess whether or not the event is serious using the definition given in Table 4. If the event is classified as 'serious' then an SAE form must be completed and CCTU notified immediately (within 24 hours) unless the event is listed in section 6.1.2.1 as a 'foreseeable

SAE' which is **not causally related** to the trial intervention (NEL) in which case, it should be reported within 5 working days.

6.4.1.2 Severity or Grading of Adverse Events

The severity of all AEs (serious and non-serious) in this trial should be graded using the gradings in the Common Terminology Criteria for Adverse Events (CTCAE) Version 5.0 (2017):

Grades for AEs according to the CTCAE are:

Grade 1: Mild; asymptomatic or mild symptoms; clinical diagnostic observations only; intervention not indicated.

Grade 2: Moderate; minimal, local or non-invasive intervention indicated.

Grade 3: Severe or medically significant but not life threatening; hospitalisation or prolongation of hospitalisation indicated; disabling.

Grade 4: Life threatening consequences; urgent intervention indicated.

Grade 5: Death related to AE.

6.4.1.3 Causality

The investigator must assess the causality of all serious events in relation to the intervention (NEL) using the definitions in Table 5.

Table 5: Causality Definitions

Relationship	Description
Unrelated	There is no evidence of any causal relationship
Related	There is clear evidence to suggest a causal relationship to the intervention and other possible contributing factors can be ruled out

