6.1.1 Adverse Events

Adverse events include:

- an exacerbation (i.e., increase in the frequency or intensity) of a pre-existing illness, episodic event or symptom (initially recorded at the screening/baseline visit), that is detected after trial intervention
- occurrence of a new illness, episodic event or symptom, that is detected after trial intervention

Adverse events do NOT include:

- Medical or surgical procedures: the condition that leads to the procedure is the adverse event
- Pre-existing disease or a condition present before treatment that does not worsen
- Hospitalisation where no untoward or unintended response has occurred

Reporting of Adverse Events

The patient population includes preterm infants who are cared for on a neonatal intensive care for a prolonged period. Due to the nature of the patient population, a high incidence of adverse events can be foreseeable during their hospital stay. Only adverse events deemed as serious (see section 6.1.2) or as notifiable event (see section 6.2) will be recorded for the trial.

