6.4.1.4 Expectedness

If there is at least a possible involvement of the trial intervention (NEL), the sponsor will assess the expectedness of the event. If information of expectedness is provided by the investigator this should be taken into consideration by the sponsor. An unexpected adverse event is one not reported in Table 6 NEL Risks and mitigations (**Section 6.3.1.5**).

6..1.5 Risks associated with NEL

The risks associated with NEL for the ENLIVEN-UK trial are listed in Table 6 (NEL risks and mitigations) below:

Table 6. NEL risks and mitigations.

POTENTIAL RISK	RISK MANAGEMENT
Infection	Procedure in strict sterile conditions in operating theatre as per standard practice. Peri-operative antibiotics are given and the choice of agent and duration will vary according to local guidelines.
Secondary bleeding	There is a clear consensus on surgical protocol to ensure maximal safe washout without causing secondary bleeding in the ventricles or in the brain. The surgeon should stop when they feel they have achieved a 'maximal safe washout' as defined in the consensus guideline (28).
Stroke	Procedure-related brain injury risk has not been reported with NEL and therefore, the

	risk is low. It will be identified if it occurs on
	the post-operative ultrasound scan.
CSF leak	Standard closure techniques will be used to
	protect against CSF leak and, if it develops,
	will be managed at the discretion of the
	treating surgeon.
Seizures	Seizures (up to CTCAE Grade 3) can arise
	as a result of the initial IVH or procedure-
	related brain injury. These have been
	reported with NEL but the risk is low. If it
	occurs, it will be managed at the discretion of
	the treating medical team including
	neurosurgeon and neonatologist.
Temporising device dysfunction	The TD may stop working adequately due to
	either blockage, insufficient drainage or
	infection. At this stage, the clinical team will
	make an assessment as to whether it needs
	to be revised or whether a permanent
	ventriculoperitoneal shunt needs to be
	placed. This management will remain at the
Flootrolyte/Codings imbalance	discretion of the treating neurosurgical team.
Electrolyte/Sodium imbalance	The use of irrigating solution may lead to
	disturbances in the serum level of sodium
	and other electrolytes. This will be mitigated
	by using appropriate irrigating solutions, such
	as Ringer Lactate or artificial CSF and by
	monitoring electrolyte levels in the serum as

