6.4.2 Notifications

6.4.2.1 Notifications by the Investigator to CCTU

CCTU must be notified of all SAEs excepting those listed in 6.1.2.1 - unless considered **causally related** to the intervention immediately after site staff become aware of the event (in no circumstances should this notification take longer than 24 hours).

The Foreseeable (expected) SAEs listed in section 6.1.2.1 must be reported within 24 hours of site staff becoming aware of them **if they are considered causally related** to the trial intervention (NEL).

'Foreseeable SAEs' that are **not considered causally related** to the trial intervention (NEL) should be reported within 5 working days using the SAE report form.

All 'Unforeseeable SAEs' i.e., all other SAEs occurring in trial participants which are not detailed in Section 6.1.2.1 should be reported within 24 hours of site staff becoming aware of them using the SAE report form.

All Notifiable AEs (NAEs) listed in Section 6.2 should be reported within 5 working days using the Notifiable Adverse Events (NAE) CRF.

Investigators should notify CCTU of any SAEs and Notifiable Adverse Events (NAEs) occurring from the time of randomisation until 2-year hospital visit follow up. From this point forward the site will not actively monitor SAEs or NAEs.

The SAE form must be completed by the site staff named on the delegation log with this responsibility assigned by the PI. The form should be reviewed and signed off by the investigator (listed on the delegation log) who is responsible for the participant's care with

attention paid to the grading and causality of the event. The responsible investigator should check the SAE form at the earliest opportunity, make any changes necessary and sign. Systems should be in place at the site to enable the investigator to check the form for clinical accuracy as soon as possible.

The minimum criteria required for reporting an SAE are the primary event term, participant's trial specific PIN, date of birth, name of reporting investigator and sufficient information on the event to confirm seriousness. Any further information regarding the event that is unavailable at the time of the first report should be completed as soon as it becomes available.

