6.4.2.2 UCL CCTU responsibilities

Clinical reviewer (Chief Investigator, or a medically qualified delegate) will review all SAE reports received. The causality assessment given by the local investigator at the hospital cannot be overruled; in the case of disagreement, both opinions will be provided in any subsequent reports.

The clinical reviewer will complete the assessment of expectedness using table 6 (NEL risks and mitigations) in **section 6.3.1.5.**

CCTU is undertaking the duties of trial sponsor and is responsible for the reporting of SAEs occurring to research participant where in the opinion of the clinical reviewer the event was related and unexpected, to the REC within 15 days of the sponsor becoming aware of the event.

CCTU will keep investigators and the IDMC informed of any safety issues that arise during the course of the trial.

In the UK, an Annual Progress Report (APR) will be submitted to the REC within 30 days of the anniversary date on which the favourable opinion was given, and annually until the trial is declared ended.

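### Table 5 has no causality grade for a possible or probable link to NEL, conflicts with section 6.4.1.4, and can slow the reporting of some foreseeable SAEs

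*Protocol*

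**What the plan says.** Protocol section 6.4.1.3 is mandatory in tone and covers every SAE: "The investigator must assess the causality of all serious events in relation to the intervention (NEL) using the definitions in Table 5". Table 5 then offers two grades. Unrelated reads "There is no evidence of any causal relationship". Related reads "There is clear evidence to suggest a causal relationship to the intervention and other possible contributing factors can be ruled out".

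The next subsection, 6.4.1.4, uses another threshold: "If there is at least a possible involvement of the trial intervention (NEL), the sponsor will assess the expectedness of the event".

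Two reporting rules depend on the grade:

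- **Site to CCTU (section 6.4.2.1).** For events judged causally related, "The Foreseeable (expected) SAEs listed in section 6.1.2.1 must be reported within 24 hours of site staff becoming aware of them". Foreseeable SAEs judged not causally related "to the trial intervention (NEL) should be reported within 5 working days using the SAE report form".
- **CCTU to REC (section 6.4.2.2).** The 15-day report applies "where in the opinion of the clinical reviewer the event was related and unexpected". Expectedness is judged against Table 6, the list of NEL risks.

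**The concern.** Most real causality judgements lie between no evidence and proof with every alternative excluded. Table 5 leaves that middle ground without a grade, and the adjacent subsection assumes that it has one.

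The gap matters more here than in many trials, because the protocol itself describes competing causes as usual. Every Arm A infant receives a temporising device in the same operation, and section 1.4 lists largely the same risks for the device and for NEL: infection, haemorrhage, seizures, CSF leak and electrolyte disturbance. Table 6 attributes seizures either to the initial haemorrhage or to the procedure. Section 6.2 notes that preterm infants have many possible sources of infection. A grade that requires other contributors to be excluded will therefore be hard to reach.

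At stake is how quickly the sponsor learns of some serious events to which NEL may have contributed, and whether some of them reach the REC. Safety of NEL is part of the trial's stated objective (section 1.2).

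**Working it through.** No formula applies. The check sets Table 5 against each rule that could use it.

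**Step 1: do the two grades cover all cases?** Unrelated needs an absence of any evidence. Related needs clear evidence and the exclusion of other contributors. An event with some evidence, or with clear evidence and a competing cause, satisfies neither. No section says which grade such an event should receive.

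**Step 2: does section 6.4.1.4 agree with Table 5?** It starts the expectedness step at possible involvement of NEL. Table 5 cannot record that level, so the two subsections set different thresholds for the same pathway.

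**Step 3: which reporting routes depend on the grade?**

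| Route | Timing | Depends on Related? |
|---|---|---|
| SAE on the foreseeable list (6.1.2.1, 6.4.1.1, 6.4.2.1) | 24 hours if related, 5 working days if not | Yes |
| Unforeseeable SAE, site to CCTU (6.1.2.2, 6.4) | 24 hours | No |
| Notifiable AE (6.2) | 5 working days | No |
| Death, to the IDMC (6.5) | Promptly once CCTU is told | No |
| CCTU to REC (6.4.2.2) | 15 days, if related and unexpected | Yes, if the clinical reviewer applies Table 5 |

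**Step 4: does the affected route contain plausible NEL harms?** The foreseeable list in 6.1.2.1 includes intraventricular haemorrhage on imaging, seizures beyond 48 hours of the procedure, and sepsis. These overlap Table 6's secondary bleeding, seizures and infection. The exposure is confined to Arm A (planned 50 of 100 infants), because 6.1.2.1 treats all foreseeable SAEs in Arm B as unrelated to NEL.

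**Step 5: one hypothetical event followed through.** An Arm A infant has a CTCAE grade 4 seizure at 72 hours.

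1. It is beyond 48 hours, so it is on the foreseeable list and 24-hour reporting needs the grade Related.
2. The initial haemorrhage cannot be excluded as a cause, so Table 5's Related is not met.
3. If the site codes it Unrelated, CCTU hears within 5 working days.
4. Table 6 covers seizures up to grade 3, so grade 4 can be read as unexpected. If the clinical reviewer applies Table 5, the event is not related and no 15-day REC report follows.
5. On the possible-involvement threshold of 6.4.1.4, the same event could qualify for both the 24-hour report and the REC report.

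The handling of the event turns on which of two adjacent subsections is followed.

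**The case against.** The strongest reply is that 24-hour reporting is the default. Under 6.4.1.1 a serious event leaves that route only if it is both on the foreseeable list and not causally related. Stroke, CSF leak and electrolyte imbalance, all in Table 6, are not on that list, and neither are seizures within 48 hours. When serious, they go to CCTU within 24 hours whatever the grade. This stands. A reader might infer that NEL-related events will rarely be expedited, and the protocol does not support that.

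It can also be said that nothing sends an ungraded event to Unrelated, and that an event with some evidence of a link fails that definition too. This stands as well: the text leaves the choice open, so the slower route is a risk, not a certainty.

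On the REC report, the trigger is the clinical reviewer's opinion. Although 6.4.2.2 does not let the reviewer overrule the site, both opinions are reported. Haemorrhage, infection and seizures up to grade 3 are in Table 6 and would generally be expected, so no 15-day report would be due under any definition of Related. This limits the REC consequence to events outside Table 6.

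Two further inferences fail. One is that harm signals may never reach the sponsor. All SAEs reach CCTU, at worst in 5 working days, and the IDMC has unrestricted unblinded data (8.3.3), so it can compare arms without relying on attribution. The other is that a published count of related SAEs would be biased. The safety outcome in 5.1.2 is a number of adverse events, and no count by attribution is specified.

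None of this closes the gap in Table 5 or removes the conflict with 6.4.1.4. The lower threshold in 6.4.1.4 helps only if the reviewer uses it, and the protocol gives the reviewer no causality definition other than Table 5.

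**Conclusion.** The defect is on the face of the text: two grades that do not cover all cases, and a neighbouring rule that uses a level they omit. The size is bounded:

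- **Timing.** For foreseeable-list SAEs in Arm A to which NEL may have contributed, notification to CCTU may take 5 working days instead of 24 hours.
- **REC report.** Events outside Table 6 may miss the 15-day report.

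The first consequence assumes that sites code some intermediate events as Unrelated. The second assumes that the clinical reviewer applies Table 5. The protocol neither requires nor prevents either. How many events are involved cannot be estimated from the document. Between-arm totals are unaffected.

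Two grades are not in themselves an error. The fault lies in where the boundary is drawn and in the inconsistency.

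**What to change.** In Table 5, define Related as at least a reasonable possibility that NEL caused or contributed to the event, and let everything else be Unrelated. This keeps two grades, covers every case and matches the threshold in 6.4.1.4. A graded scale would also work if possible and above counted as related, but it is not needed.

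Align sections 6.1.2, 6.4.1.4 and 6.4.2 and the SAE form with the new definition. Then re-check the causality coding of foreseeable SAEs already reported, so that one standard applies throughout the trial.

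The cost is a protocol amendment, a form change, a limited retrospective check, and somewhat more 24-hour reports from sites.

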6.4.1.4 Expectedness

If there is at least a possible involvement of the trial intervention (NEL), the sponsor will assess the expectedness of the event. If information of expectedness is provided by the investigator this should be taken into consideration by the sponsor. An unexpected adverse event is one not reported in Table 6 NEL Risks and mitigations (**Section 6.3.1.5**).

6..1.5 Risks associated with NEL

The risks associated with NEL for the ENLIVEN-UK trial are listed in Table 6 (NEL risks and mitigations) below:

Table 6. NEL risks and mitigations.

POTENTIAL RISK	RISK MANAGEMENT
Infection	Procedure in strict sterile conditions in operating theatre as per standard practice. Peri-operative antibiotics are given and the choice of agent and duration will vary according to local guidelines.
Secondary bleeding	There is a clear consensus on surgical protocol to ensure maximal safe washout without causing secondary bleeding in the ventricles or in the brain. The surgeon should stop when they feel they have achieved a 'maximal safe washout' as defined in the consensus guideline (28).
Stroke	Procedure-related brain injury risk has not been reported with NEL and therefore, the

	risk is low. It will be identified if it occurs on
	the post-operative ultrasound scan.
CSF leak	Standard closure techniques will be used to
	protect against CSF leak and, if it develops,
	will be managed at the discretion of the
	treating surgeon.
Seizures	Seizures (up to CTCAE Grade 3) can arise
	as a result of the initial IVH or procedure-
	related brain injury. These have been
	reported with NEL but the risk is low. If it
	occurs, it will be managed at the discretion of
	the treating medical team including
	neurosurgeon and neonatologist.
Temporising device dysfunction	The TD may stop working adequately due to
	either blockage, insufficient drainage or
	infection. At this stage, the clinical team will
	make an assessment as to whether it needs
	to be revised or whether a permanent
	ventriculoperitoneal shunt needs to be
	placed. This management will remain at the
Flootrolyte/Codings imbalance	discretion of the treating neurosurgical team.
Electrolyte/Sodium imbalance	The use of irrigating solution may lead to
	disturbances in the serum level of sodium
	and other electrolytes. This will be mitigated
	by using appropriate irrigating solutions, such
	as Ringer Lactate or artificial CSF and by
	monitoring electrolyte levels in the serum as
	in routine post-operative practice in neonatal
	care.

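### Expectedness is tied to Table 6, where only the seizures row mentions severity, so a NEL-related life-threatening or fatal bleed or infection is not required to go to the REC within 15 days

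*Protocol*

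**What the plan says.** Protocol section 6.4.1.4 (Expectedness) gives the rule: "An unexpected adverse event is one not reported in Table 6 NEL Risks and mitigations". Section 6.4.2.2 (UCL CCTU responsibilities) puts it into use: "The clinical reviewer will complete the assessment of expectedness using table 6 (NEL risks and mitigations". The same section sends an SAE to the REC on the expedited clock only where "in the opinion of the clinical reviewer the event was related and unexpected, to the REC within 15 days of the sponsor becoming aware".

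Table 6, directly below 6.4.1.4, lists seven risks: infection, secondary bleeding, stroke, CSF leak, seizures, temporising device dysfunction, and electrolyte or sodium imbalance. One row mentions severity: "Seizures (up to CTCAE Grade 3) can arise". The others describe mitigation or management only. The infection row opens "Procedure in strict sterile conditions in operating theatre as per standard practice" and the bleeding row "There is a clear consensus on surgical protocol to ensure maximal safe washout without causing secondary bleeding in the ventricles or in the brain". The stroke row says that procedure-related brain injury has not so far been reported with NEL.

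Section 6.4.1.2 defines CTCAE grades 1 to 5, ending with "Grade 5: Death related to AE", and applies them to all adverse events. It does not mention expectedness.

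**The concern.** Whether an event was expected should depend on its severity and outcome as well as its type. A small, self-limiting bleed after lavage and a fatal one share a name but say very different things about the procedure. The rule in 6.4.1.4 does not separate them.

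At stake is the expedited external route for safety signals. Section 1.2 makes safety part of the trial's objective. Section 4.1 calls NEL novel in this context, and section 1.1.1 reports a single-centre pilot of 17 infants with a median weight of 886 g at NEL. If the worst forms of the main procedural risks count as expected because the risk is listed at all, the REC need not hear of them within 15 days.

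**Working it through.** There is no figure to reproduce, so the check traces the rule through the text.

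**Step 1: count the rows.** Table 6 has 7 risks, of which 1 (seizures) mentions a grade. 7 − 1 = 6 have no severity limit.

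**Step 2: fix the reporting condition.** Under 6.4.2.2, 15-day REC reporting needs a serious event AND related AND unexpected. Under 6.4.1.4, unexpected means not reported in Table 6.

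**Step 3: apply it to NEL-related grade 4 or 5 events.** The rule can be read in two ways: only the risk's name counts, or the row's text counts too.

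| Event | Name only | Row text counts |
|---|---|---|
| Secondary bleeding | listed, so expected: no 15-day report required | no limit in the row, so expected: no 15-day report required |
| Infection | same | same |
| Stroke | same | no limit; row says not reported with NEL, so arguable |
| Seizure | listed, so expected: no 15-day report required | above the grade in the row, so unexpected: 15-day report |

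For bleeding and infection the answer is the same on both readings. The contrast with seizures appears only on the second. On the first, even the seizure limit has no effect. Neither reading makes severity count across the table.

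**Step 4: look for another route that closes the gap.**

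- *Trials unit.* Every NEL-related SAE reaches CCTU within 24 hours, whether on the foreseeable list or not (6.1.2.1, 6.4, 6.4.2.1). CCTU acts for the sponsor, so this is not external review.
- *IDMC.* It is told promptly of every death (6.3, 6.5), reviews SAEs (6.5), has unrestricted access to unblinded data (8.3.3) and is to be kept informed of safety issues (6.4.2.2). Only deaths have a prompt, case-by-case rule, and the IDMC is not the REC.
- *Annual Progress Report to the REC* (6.4.2.2). Yearly.
- *Urgent safety measures* (6.4.2.3). The REC has written notice within 3 days, but only if such a measure is taken.

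So a related, life-threatening, non-fatal bleed or infection has no required expedited route to the REC unless an urgent safety measure follows. A related death goes promptly to the IDMC, but has no required 15-day REC report if its cause is a listed risk without a limit.

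**Step 5: is the gap deliberate?** Nothing says so. Section 6.2 attaches CTCAE thresholds to six of its seven notifiable events, and the seizures row shows that severity was considered once in Table 6. No reason is given for leaving the other six rows open.

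**The case against.** The best case for the plan has four parts.

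**Reviewer judgement.** REC reporting turns on the clinical reviewer's opinion, and 6.4.1.4 says that any view from the investigator on expectedness should be considered. A reviewer could also note that no row of Table 6 describes a fatal outcome. A reader might infer from the rule that a severe listed event can never reach the REC within 15 days. The text does not go that far: such a report is not required, but neither is it forbidden. Still, the reviewer is told to use Table 6, so reporting a fatal bleed as unexpected would depart from the written definition.

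**The seizure grade.** It sits in the risk-management column and is not labelled as a limit on expectedness. This is fair, and it is why the contrast with seizures is only arguable. The main point does not depend on it.

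**Other oversight.** A reader might infer that these events escape the REC, or all external review. They do not: the annual report and the IDMC remain. What is missing is one expedited route.

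**The causality gate.** Table 5 allows an event to be called related only on clear evidence with other contributing factors ruled out. In preterm infants who already have IVH, few bleeds or infections may pass, so the amendment may change few reports. That limits the number. It also means that an event which does pass is a strong signal.

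**Conclusion.** The point holds as a drafting fault in a stated safety rule. Six of seven listed risks have no severity limit, and following 6.4.1.4 and 6.4.2.2 as written leaves NEL-related grade 4 or 5 bleeding and infection, and on the plainer reading stroke, outside required 15-day REC reporting. This assumes that the reviewer applies the written definition and does not use discretion against it.

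Two further inferences are not supported. One is a count of affected infants: section 1.4 puts the additional risks below 5%, but that covers any severity and does not say whether it is per risk or overall. The documents give no rate for related grade 4 or 5 events, so the number cannot be estimated. The other is that NEL is an entirely new operation: section 4.1 says that neurosurgeons already know the procedure and that it is novel only in this setting.

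The amendment should be made because it is cheap and the events concerned are the gravest. Trial validity and the primary analysis are not affected.

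**What to change.** Two changes to the Protocol:

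1. Add a column to Table 6 in which the sponsor states the maximum expected CTCAE grade for every row. The grades are for the sponsor to set.
2. Replace the definition in 6.4.1.4 with: *An event is unexpected if it is not listed in Table 6, or if it is more severe than the grade stated there; a fatal or life-threatening NEL-related event is unexpected unless its row expressly lists that severity.*

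The closing condition in the second change keeps the two halves from conflicting if the sponsor sets a row at grade 4 or 5.

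In the same amendment, reconcile the wording with Table 4 and section 6.1.2, which also use the terms expected and unexpected, but for a different list that governs how fast sites report to CCTU.

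Cost: one column, one sentence and a few more 15-day reports. Treatment, data collection and sample size do not change.
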